Primary breast cancer is a heterogeneous disease, with multiple pathologic and molecular subtypes and varying clinical outcomes. Currently, immunohistochemical (IHC) markers for estrogen receptors (ER) and progesterone receptors (PR) and the HER2 epidermal growth factor receptor are used to classify 4 different clinical subtypes of breast cancer: 1) ER+ and/or PR+, HER2-; 2) ER+ and/or PR+, HER2+; 3) ER-, PR-, HER2-; and 4) ER-, PR-, HER2+. However, global gene expression profiling studies have recently identified 4 main molecular signatures that correspond to the 4 clinical subtypes respectively: luminal A and B (hormone receptor positive), basal-like ("triple-negative"), and HER2 enriched (HER2+) (**Figure 1**).⁸⁻¹¹ A fifth subtype, the normal breast tissue-like group, was also identified. However, the clinical significance of this group is not known and may represent poorly sampled tumor.⁸ Clinical outcomes vary between the different subtypes; the luminal A group has the best prognosis and the basal-like and HER2 enriched subtypes are associated with an inferior overall and disease free survival.^{8, 10-11}

To our knowledge, no studies have identified the gene expression profile of breast cancers arising in the context of childhood exposure to thoracic radiotherapy for previous malignancies. Since each molecular subtype carries a different clinical outcome and treatment strategy, this knowledge may guide therapeutic decisions and estimation of patient prognosis as well as improve our understanding of radiation-induced oncogenesis in breast tissue.

Specific aims/objectives/research hypotheses/methods:

Our overriding hypothesis is that radiation interacts, enhances, and potentially accelerates the individual patient's genetic predisposition to develop breast cancer, but does not fundamentally alter the molecular phenotype. To test this hypothesis, we plan to obtain the 54 (or more if available) formalin-fixed, paraffin-embedded tissue samples of the secondary breast cancer cases from the CCSS bio-repository from women who received thoracic radiation. We plan to subject these samples to RNA extraction, using established protocols that yield expression profiles that are highly concordant with frozen tissue.¹²⁻¹³ This mRNA will then be assayed for quality and quantity and amplified accordingly.¹⁴ The resultant cDNA will then be hybridized, at our core facility, using the Affymetrix U133A gene chip. Using the GeneSpring software platform, gene expression data will then be analyzed using supervised methods (which will query the expression levels of specific, hallmark genes that define the molecular subtypes of breast cancer) as well as unsupervised methods (within the set of 54 cases as well as in conjunction with 1,619 general population cases) to determine the prevalence of known, and potentially novel, molecular subclasses of these secondary tumors. Once the subclass designation is established for the 54 secondary breast cancers, the patient demographics and overall survival time after diagnoses will be compared to their spontaneous/general population

counterparts. Generating this working data will enable us to answer the following clinically important questions, which represent our specific aims:

- Specific Aim 1: What is the prevalence/distribution of Luminal A, Luminal B, Basal, Her2-enriched and breast-like breast cancer subtypes among those women who received thoracic radiation during childhood for their pediatric malignancy versus that observed in the general population of spontaneous breast cancers? Consistent with our overriding hypothesis is that the prevalence of these molecular subtypes will approximate that observed in the general, spontaneous breast cancer population. Therefore, assuming radiation induced breast cancers are representative of the general population, approximately 50% will be Luminal A, 20% will be Luminal B, 20% will be Basal, and 10% will be Her 2+.
- 2. Specific Aim 2: Is there a clinical outcome difference in terms of overall survival after diagnosis within the molecular subclasses of the 54 cases of secondary breast cancers from the childhood cancer survivors and compared to spontaneous breast cancers from the general population cases with the same molecular subclass? We believe the answer to this question will determine if radiation has an independent role in expediting the development of various breast cancers and/or augmenting the biologic lethality of the disease.

If our overriding hypothesis is incorrect, then 2 other potential phenomena may be identified with this data:

- 1. Radiation to the chest during childhood induces a specific type of one of the established molecular subclasses of breast cancer, which may or may not have the same virulence as seen in the general breast cancer population.
- 2. A novel molecular subclass(es), unique to patients with radiation to the chest during childhood, is elucidated. If so, multiple questions can be answered using this data:
 - i. What are the hallmark genes that define this group?
 - ii. What are the patient demographics at time of onset? And
 - iii. What is the expected survival time within this group(s)?

Analysis framework:

Outcome of interest

Primary endpoint:

- The patterns of gene expression and distribution of molecular subtypes of radiation induced breast cancer compared to spontaneous/primary breast cancer

Secondary endpoints:

- Overall survival: Time from diagnosis of breast cancer to death of any cause
- Patient demographics at the time of breast cancer diagnosis.

Subject population:

Inclusion criteria

- 1. Cases: Survivors from the Childhood Cancer Survivor Study Cohort who subsequently developed breast cancer after thoracic radiation, with available breast tissue
- 2. Controls: 1,619 patients with spontaneous primary breast cancers, without previous cancer diagnosis or treatment, obtained from previously published research studies for which the gene expression data is publically available, will comprise the general, spontaneous breast cancer population. The previously published gene expression data is analyzed for subtype composition and is presented in **Figure 2**.¹⁵⁻²²
 - a. All ages
 - b. All stages
 - c. Tumor sample obtained from biopsy or surgical specimen prior to any non-surgical therapy
 - d. Biopsy proven invasive ductal, lobular, mucinous, tubular, colloid or papillary (i.e. epithelial) carcinoma of the breast
 - e. Primary and secondary breast cancer with any hormone status, including ER+, PR+/-, Her2neu-; ER+,PR+/-, Her2neu +; ER-,PR-, Her2neu-; ER-/PR-, Her2neu +

Exclusion criteria

- 1. Previously published research using gene expression data sets for primary breast cancers previously treated with chemotherapy, hormone therapy, or radiation prior to analysis will not be used for the control population
- 2. Previously published research using gene expression data from cell lines and animal studies will not be used for the control population
- 3. Non-epithelial breast malignancies, including lymphoma or sarcoma of the breast and melanoma and non-melanomatous skin cancers
- 4. In situ carcinomas of the breast

Materials/Data needed from the CCSS

- 1. Adequate secondary breast cancer tissue, from the study patients, to yield sufficient, amplifiable mRNA for eventual hybridization with the Affymetrix U133A Gene Chip.
 - a. N=54 (or more if possible)
 - b. At least five 10-micron scrolls (or equivalent quantity) of tumor tissue, verified by corresponding H&E slide, for each sample
- 2. Clinical data on study patients:
 - a. Age at childhood cancer diagnosis
 - b. Childhood primary tumor diagnosis
 - c. Childhood radiotherapy details (including total body irradiation and pelvic radiotherapy)
 - i. Dose and fractionation to irradiated site

- ii. Radiation dose to the chest
- iii. Age at start of radiation
- d. Age at breast cancer diagnosis
- e. Menopausal status at breast cancer diagnosis
- f. Age at death or last follow-up with current vital status for survival calculations
- g. Use of chemotherapy for treatment of the primary cancer

Statistical and Analytic Plans:

The first layer of analysis will consist of determining the distribution of the molecular subtypes of the secondary breast cancers. The RNA will be isolated from the study samples and in a manner similar to the clustering analysis of the control population, the gene expression status of the 249 genes that define the molecular subclasses will be performed in an unsupervised manner on the 54 study and 1,619 control cases together. To account for batch-effect and paraffin extraction, log-transformation and normalization using the RMA method will be performed, again using GeneSpring software, with all cases included. Genes will undergo an independent QA process (to determine if there is signal susceptibility to the formalin fixation and parafinization process) and will be excluded from the final clustering analysis. The placement of the study cases within the cluster groups, as defined predominantly by the control population, will determine the subclass assignment. A chi-square test will be used to compare the distribution of molecular subtypes between the primary and secondary breast cancers.

The raw data from the .cel files of the study population will also be compared. This will be especially important in the event of the formation of a separate clustering group by the radiation-induced cases and a novel subtype is identified. From this analysis, the genes that define this new subclass will be identified and reported. This approach will also allow the identification of gene expression, unique to previously radiated breast tissue, which spans across all subtypes.

To study our second aim, the molecular subtype status of the study population will be analyzed as a clinicopathologic factor for it's association with survival as well as with other factors such as age at childhood cancer diagnosis, type of childhood primary malignancy, age at time of radiation for childhood malignancy, radiation dose to the chest during childhood, total radiation dose received during childhood, use of chemotherapy for treatment of childhood malignancy, age and menopausal status at breast cancer diagnosis, and stage at breast cancer diagnosis. Correlative analysis (Spearman's rho, t-tests, ect.) will be used to test for univariable associations between the molecular subtype and the cross-sectional demographic variables. For the time-to-event outcomes such as survival and time to onset of breast cancer the log-rank test will be used to determine univariate associations of the molecular subtype (key risk factor of interest) with these outcomes intervals. Additional risk factors such as age at childhood cancer diagnosis, age at time of radiation for childhood malignancy, and radiation dose to the chest during childhood will also be evaluated similarly. Cox proportional hazards models will be used to evaluate multivariable associations between molecular subtype and each of the time-to-event outcomes, adjusting for other factors found to be significant in univariable analyses, or considered *a priori* to be important to include in the model (e.g. age at diagnosis, breast cancer stage, etc.)

The CCSS database represents the only chance in which the issue of the breast cancer molecular subclass prevalence, in the setting of previous thoracic radiation, could possibly be addressed. If any single institution attempts to do this, there would not be enough cases to draw a statically significant conclusion. Fortunately, there are 54 cases within the CCSS database, and this is sufficient to determine if the 5 molecular subtypes are evenly distributed, or predominately composed of 1 or 2 subtypes. In the most diffuse scenario, if there are at least 10 samples per subtype (5), there will be a >80% power to detect a 2-fold difference between any of the two groups using Chi-squared analysis. A coefficient of variation of 50% and alpha = 0.005 (.05/10, to adjust for 10 comparisons between 5 groups) will be used for the calculations. Since we expect there to be 50% with the Luminal A subtype designation, there will be even greater power to make this conclusion statistically valid. It should be iterated, though, that regardless of statistical power, this is a retrospective study and the large number of subjects from the CCSS provide the only means for attempting to answer this scientific question.

Figures:

Hierarchical clustering of 115 tumour tissues and seven non-malignant tissues using the "intrinsic" gene-set. (A) A scaled-down representation of the entire cluster of 540 genes and 122 tissue samples based on similarities in gene expression. (B) Experimental dendrogram showing the clustering of the tumours into five subgroups. Branches corresponding to tumours with low correlation to any subtype are shown in grey. (C) Gene cluster showing the *ERBB2* oncogene and other co-expressed genes. (D) Gene cluster associated with luminal subtype B. (E) Gene cluster associated with the basal subtype. (F) A gene cluster relevant for the normal breast-like group. (G) Cluster of genes including the oestrogen receptor (*ESRI*) highly expressed in luminal subtype A tumours. Scale bar represents fold-change for any given gene relative to the median level of expression across all samples. PNAS, July 8, 2003, vol. 100, no. 14, 8418–8423. Copyright (2003) National Academy of Sciences, USA.

Figure 1: Molecular subtypes of breast cancer identified. Gene expression profiles of primary breast cancers demonstrating 5 distinct molecular subtypes: luminal A, luminal B, Basal, ERBB2+ (HER2 enriched [ERBB2+]), and normal breast-like. From Perou CM et al. Molecular portraits of human breast tumours. Nature 2000;406:747-52.

Figure 2: Our preliminary data. Supervised clustering analysis using 249 genes identified as hallmark genes in determining the established molecular subtypes applied to 1,619 cases from publicly available U133A-derived .cel files,¹⁵⁻²² after log-transformation and normalization using the RMA method. The approximate subclass designation is noted (scaling precludes detailed dendrogram). Collectively, these cases reflect an adequate, heterogeneous control population. Data obtained from radiation-induced breast cancers will be analyzed within the context of this general population of spontaneous breast cancers.

Special considerations:

The principle investigator has significant experience in extracting RNA and DNA from paraffin-embedded tissues for global profiling analyses.²³⁻²⁵

References:

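### Aim 1 hypothesises that subtype shares resemble the general population, but the only test of the distribution is a chi-square for difference, which cannot support that hypothesis

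*Protocol*

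**What the plan says.** All references are to the protocol.

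- **Hypothesis (Specific aims).** Radiation may interact with, enhance or accelerate a genetic predisposition but "does not fundamentally alter the molecular phenotype". The tissue is to be obtained in order to test this.
- **Specific Aim 1.** The aim asks how subtype prevalence in cases compares with that in spontaneous cancers. Under the hypothesis the prevalence of these "molecular subtypes will approximate that observed in the general, spontaneous breast cancer population", that is, "approximately 50% will be Luminal A, 20% will be Luminal B, 20% will be Basal, and 10% will be Her 2" positive. No margin is attached to the word approximate.
- **Analysis framework.** The subtype distribution, compared with spontaneous cancers, is part of the primary endpoint.
- **Statistical and Analytic Plans, first paragraph.** Clustering is run "in an unsupervised manner on the 54 study and 1,619 control cases together". Then: "A chi-square test will be used to compare the distribution of molecular subtypes between the primary and secondary breast cancers". No other test of the distribution is named.
- **Statistical and Analytic Plans, last paragraph.** Of the 54 cases: "this is sufficient to determine if the 5 molecular subtypes are evenly distributed, or predominately composed of 1 or 2 subtypes". With 10 samples in each of five subtypes, "there will be a >80% power to detect a 2-fold difference between any of the two groups using Chi-squared analysis", using a coefficient of variation of 50% and alpha 0.005. The paragraph adds that the expected 50% Luminal A share gives still more power to make the conclusion valid.

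**The concern.** The null hypothesis of the chi-square test is that cases and controls share one distribution, which is in substance the study's own hypothesis. Rejection would count against that hypothesis. Non-rejection only says that 54 cases did not show a difference. The text following Specific Aim 2 sets out what may be found if the hypothesis is wrong, but nothing sets out what would count in its favour.

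The adequacy argument does not close this gap. Whether subtypes are evenly spread or concentrated within the cases is a question about one group. Aim 1 compares two groups, and the pattern expected under the hypothesis is itself uneven. Finding an uneven spread therefore says nothing about agreement with controls.

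The protocol's introduction says that subtype knowledge may guide treatment and prognosis, and that basal-like and HER2-enriched cancers do worse. A conclusion of unchanged phenotype that rested on non-significance could hide a moderate excess of those subtypes.

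**Working it through.** **Inputs.** Cases 54 and controls 1,619 (protocol). Control shares p = 50/20/20/10% for Luminal A / Luminal B / Basal / HER2. This is an assumption: the protocol gives these shares as the expected pattern, and the observed control shares are in a figure that is not shown. The four shares sum to 100%, so the normal-like class is left out and the test has 3 df. Two-sided alpha is 0.05 (assumed).

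**1. The protocol's own power figure.** With 10 per group, a two-fold difference in means, SD equal to half the lower mean and two-sided alpha 0.005, power is 95.2% (normal) or 87.8% (noncentral t). So the claim of more than 80% is reached under this reading, which compares two means. A chi-square on two proportions with 10 per group at alpha 0.005 gives 3% for 20% v 40% and 39% for 50% v 100%. Either way the figure concerns detecting a difference, not showing agreement.

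**2. The even-spread question.** Testing 50/20/20/10/0 against 20% in each of five classes:

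λ = 54 × (0.3² + 0² + 0² + 0.1² + 0.2²)/0.2 = 54 × 0.70 = 37.8, with 4 df, so power is 99.97%.

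The sample is ample for that question, but the answer does not bear on Aim 1.

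**3. Power of the planned case-control chi-square.** With case shares q and m = (54q + 1619p)/1673,

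λ = Σ [54(q − m)²/m + 1619(p − m)²/m].

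| Case shares (LumA/LumB/Basal/HER2) | λ | Power, simulated |
|---|---|---|
| 40/20/30/10 | 3.62 | 34% |
| 40/20/20/20 | 6.11 | 51% |
| 35/20/35/10 | 8.11 | 65% |
| 30/20/40/10 | 14.36 | 88% |
| 25/15/50/10 | 29.73 | over 99% |

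The noncentral chi-square approximation gives 33%, 53% and 66% for the first three rows.

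As an example, observed counts of 20/11/17/6 (37/20/31/11%) against 809/324/324/162 give p = 0.16. Luminal A is then 13 points lower and Basal 11 points higher than in controls, without significance.

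**4. Precision of each difference.** Half-width = 1.96 × √[p(1 − p)(1/54 + 1/1619)]:

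- 50% class: 1.96 × 0.0692 = 13.6 points
- 20% class: 1.96 × 0.0553 = 10.8 points
- 10% class: 1.96 × 0.0415 = 8.1 points

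**5. What a formal similarity test could do.** For two one-sided 5% tests with true difference 0, power = 2Φ(M/SE − 1.645) − 1, or 0 if negative. The margins M are illustrations, since the protocol gives none. For Luminal A, SE = 0.0692:

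- M = 10 points: 1.446 − 1.645 is below 0, so power is 0%
- M = 15 points: 2Φ(0.524) − 1 = 40%
- M = 20 points: 2Φ(1.247) − 1 = 79%

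These match 90% intervals. If a 95% interval must lie inside 20 points, power is 2Φ(2.892 − 1.96) − 1 = 65%, and 80% power needs a margin of about (1.96 + 1.2816) × 0.0692 = 22.4 points.

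**The case against.** **The misuse is not written down.** A reader might infer that the plan will take a non-significant chi-square as confirming similarity. No sentence says so. Aim 1 is phrased as an open comparison, and the remark about making the conclusion valid follows a statement about detecting differences. This objection stands. What remains is narrower: the hypothesis is to be tested, one test is named, and that test cannot support it.

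**The rivals to the hypothesis are gross changes.** The text after Specific Aim 2 names radiation inducing one established subclass, or a novel subclass. Concentration in one or two subtypes plausibly tracks the first of these. A reader might infer from the 34% figure that the test usually misses material shifts. The table does not support that in general: 15 points into Basal is detected more often than not, and a doubled Basal share in 88% of studies. The weakness lies in shifts of roughly 10 to 15 points.

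**A 20-point margin is no ready answer.** A reader might infer that 54 cases support 20 points for Luminal A with 95% intervals. The 79% belongs to 90% intervals. With 95% intervals it is 65%, and about 56% if all four subtypes must pass. Such a margin would also be derived from the sample size rather than from relevance.

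**Intervals and margins can sit in a SAP.** They can, and their absence alone is not the point. The hypothesis, the test and the adequacy statement are all fixed in this protocol, and they do not fit together.

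**Conclusion.** The mismatch holds. The study hypothesises approximate agreement of subtype shares, names only a test for difference, and argues sample adequacy on a question other than agreement with controls. As written, no result of the planned test could support the hypothesis. Shifts of about 10 points would be missed about two times in three and a doubling of HER2 about half the time, whereas a doubling of Basal would usually be found. These figures assume control shares of 50/20/20/10, four classes, 54 usable cases and two-sided alpha 0.05. They would worsen if fewer samples yield adequate RNA. The protocol does not commit to reading non-significance as similarity, and the chi-square is a legitimate test for difference. The fault is that nothing else is offered for a hypothesis of similarity on the primary endpoint.

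**What to change.** 1. Keep the chi-square as the test for difference.
2. Make the Aim 1 estimate the case-control difference in each subtype share, with a 95% confidence interval.
3. State that a non-significant chi-square supports only the conclusion that no difference was demonstrated, and that the intervals show which shifts remain compatible with the data.
4. Replace the sufficiency sentence in the last paragraph of Statistical and Analytic Plans with the expected half-widths: about 13.6, 10.8 and 8.1 points for classes of 50%, 20% and 10%.
5. If a formal claim of similarity is wanted, fix a margin on subject-matter grounds before the arrays are read, use two one-sided 5% tests (90% intervals), and state the power at that margin and whether every subtype must meet it.

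The cost is some rewording and a few intervals, with no further samples. The downside is a weaker permitted conclusion: unless a margin is justified and met, the study may not report that radiation leaves the subtype distribution unchanged.

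### Aim 2 credits its survival comparison with showing an independent role of radiation, but in the case-control contrast radiation and childhood cancer history cannot be told apart

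*Protocol*

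**What the plan says.** Specific Aim 2 in the protocol asks about overall survival after diagnosis in two ways: between molecular subclasses of the 54 secondary breast cancers, and "compared to spontaneous breast cancers from the general population cases with the same molecular subclass". It then gives the expected inference, introduced as the authors' belief: the answer "will determine if radiation has an independent role in expediting the development of various breast cancers", or in making the disease more lethal.

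Eligibility fixes who is compared (Subject population, Inclusion criteria):

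- Cases: "Survivors from the Childhood Cancer Survivor Study Cohort who subsequently developed breast cancer after thoracic radiation, with available breast tissue".
- Controls: "1,619 patients with spontaneous primary breast cancers, without previous cancer diagnosis or treatment". The exclusion criteria add that data sets for cancers "previously treated with chemotherapy, hormone therapy, or radiation prior to analysis will not be used for the control population".

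The Analysis framework defines overall survival from breast cancer diagnosis to death from any cause. For the cases only, the data request to the CCSS includes "Radiation dose to the chest", age at start of radiation, childhood diagnosis and "Use of chemotherapy for treatment of the primary cancer".

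The Statistical and Analytic Plans section describes Aim 2 analyses in the study population. Survival and time to onset of breast cancer are tested by log-rank against molecular subtype. Age at radiation and chest dose are evaluated in the same way. Cox models for subtype then adjust for factors that were significant univariably or judged important in advance, with age at diagnosis and stage as the examples.

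**The concern.** An independent role for radiation means an effect over and above whatever else distinguishes the two groups. The cases differ from the controls in radiation, in having had a childhood malignancy, and in whatever other treatment it received. If their survival is worse within a subclass, the protocol's sentence invites the reader to credit radiation, although the earlier disease and its other treatment are alternative explanations.

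Two features of the endpoint add to this. A late death from the childhood cancer, or from its treatment, counts as an event and would read as greater lethality of the breast cancer. And a clock that starts at breast cancer diagnosis carries no information on how quickly that cancer arose, so it cannot speak to the first half of the claim.

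**Working it through.** The protocol gives no figure for this inference, so there is none to reproduce. The question is whether the effect can be identified from the groups as defined.

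**1. Case-control contrast.** Code each subject from the eligibility criteria:

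| Group | n | Thoracic radiation | Childhood cancer |
|---|---|---|---|
| Cases | 54 | 1 | 1 |
| Controls | 1,619 | 0 | 0 |

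The design matrix [intercept, radiation, childhood cancer] has 54 + 1,619 = 1,673 rows and 3 columns. Its rank is 2, and the correlation between the last two columns is 1.0. Only the combined effect is estimable. Adding age or stage does not help, because no subject has one exposure without the other.

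An illustration with assumed hazard ratios: a case-control hazard ratio of 1.5 arises equally from

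- radiation 1.5 × other childhood-cancer effects 1.0 = 1.5;
- radiation 1.0 × other effects 1.5 = 1.5;
- radiation 1.2247 × other effects 1.2247 = 1.50.

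The data cannot choose between these.

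**2. Chemotherapy.** Childhood chemotherapy can occur only in cases, so it is associated with radiation across the two groups. It is recorded case by case, however. If some cases had none, its column differs from the radiation column and its own coefficient can be estimated. The documents do not say how many cases had it.

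**3. What the within-case dose analysis could detect.** For a Cox model with a continuous covariate, two-sided 5% level and 80% power, the detectable hazard ratio per SD is

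exp[(1.960 + 0.842) / √(d × (1 − R²))],

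where d is the number of deaths and R² is the share of dose variance explained by the adjusters. The protocol gives no death count. Assume 20% to 40% of 54, that is 10.8 to 21.6, or 11 to 22 deaths.

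| Deaths (assumed) | R² = 0 | R² = 0.3 (assumed) |
|---|---|---|
| 11 | exp(2.802/√11) = 2.33 | exp(2.802/√7.7) = 2.74 |
| 22 | exp(2.802/√22) = 1.82 | exp(2.802/√15.4) = 2.04 |

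The adjusted column is the relevant one for an analysis that controls for chemotherapy and childhood diagnosis. All of these figures depend on the assumptions.

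**The case against.** The best defence is that the plan already contains most of what is needed. The Statistical and Analytic Plans section lists chest dose, total dose, age at radiation, childhood malignancy and childhood chemotherapy as factors in the study population, and takes chest dose and age at radiation to survival and time to onset. Aim 2 itself asks partly about differences within the cases. The disputed sentence is a statement of belief about a secondary endpoint, and no test or decision rule hangs on it.

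Much of this stands. The within-case analyses are planned, so the remedy is to link and tighten them, not to invent one. What does not stand is that they support the sentence as written. It draws its conclusion from survival differences by subclass, within the cases and against controls. Comparing subclasses within the cases does not vary radiation, since every case was irradiated. Chest dose is one univariable factor among several, the Cox models are built around molecular subtype, and chemotherapy enters only if significant or chosen in advance. A separate statistical analysis plan could settle model details, but it could not undo an aliasing set by eligibility.

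Two stronger readings are tempting and should be resisted. A reader might infer that chemotherapy is as fully aliased with radiation as childhood cancer history is. The documents do not support that, because chemotherapy is collected as a variable among the cases and may differ between them. A reader might also infer that the study can say nothing about radiation at all. That overlooks the planned dose and age-at-radiation analyses, which do vary the exposure among survivors.

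**Conclusion.** The point holds in a limited form. In the case-control survival comparison, radiation and childhood cancer history are completely aliased. This follows from eligibility alone and rests on no assumption. Childhood chemotherapy is a confounder that may be partly separable. The all-cause endpoint mixes late effects of the earlier disease and its treatment into apparent breast cancer lethality, and survival from breast cancer diagnosis cannot address faster development.

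The within-case dose analysis is the better basis for a statement about radiation, but it is observational and imprecise. Under the assumed deaths and R², only hazard ratios of about 2.0 to 2.7 per SD of dose would be reliably detected after adjustment. The error is one of stated inference: the comparison itself is still worth making as a description.

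**What to change.** Reword the inference under Specific Aim 2. Suggested text: *The comparison of survival with general-population cases of the same subclass describes breast cancer after treated childhood cancer and does not isolate the effect of radiation. Statements about radiation will rest on analyses among the cases of survival and of time to onset by chest dose, adjusted for childhood chemotherapy and childhood diagnosis, reported with confidence intervals and interpreted as associations.*

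In the Statistical and Analytic Plans section, name chest dose as the exposure in that analysis and fix the two adjusters in advance, so that they do not depend on univariable significance. State that deaths from any cause include late deaths from the childhood cancer or its treatment.

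Do not write the unadjusted detectable hazard ratios into the protocol. They ignore the adjustment and rest on assumed death counts.

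The cost is a few sentences and a tighter specification of analyses already planned, on data already requested. No further tissue or comparison group is needed. The downside is a less ambitious claim and an imprecise estimate.
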